8.4 Statistical Methodology

8.4.1 Data Summary

Descriptive statistics will be computed for all baseline conditions and demographic parameters. That is, for continuous data, the N, mean, standard deviation, minimum value and maximum value will be computed. For categorical data, the frequency will be computed. The data will be presented by appropriate subgroups (e.g., center).

For all additional data collected that are not required for direct support of a study objective, data will be summarized according to visit. For parameters represented by continuous variables (e.g., BMI), the summaries will consist of the N, mean, standard deviation, minimum, and maximum values. For categorical variables (e.g., comorbidities), the frequency and percentage in each category will be presented.

Radiographic data will be presented for each visit interval at which radiographs are collected. The frequency and percentage of radiographic failures will also be presented accordingly.

Documentation of statistical analyses will be performed utilizing SAS® software version 9.3 or higher.

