4.3 Early Withdrawal of Subjects

When and How to Withdraw Subjects

In the event that the subject is discontinued by the investigative center prior to the final study evaluation, the subject will be notified by the center that he/she is no longer in the study and a Study Termination eCRF will be completed.

The following is a list of reasons for which subjects may be withdrawn and the date of termination that should be used on the Study Termination eCRF in each situation. This list is not all inclusive:

Termination Reason Date of Termination

Death Date of death

Investigative center termination Date of study close-out visit

Lost to follow-up Date Stryker termination approval given

Voluntary withdrawal Date subject notified center of withdrawal

Revision/removal of study device Date of revision/removal procedure

Study device not implanted Date of surgery

Surgery not performed Date Stryker termination approval given

At the time of study surgery, it is required that the following components are implanted to be included in the analysis:

Triathlon PSR Tibial Insert

Compatible Triathlon Tibial Baseplate

Compatible Triathlon PS Femoral Component

o Compatible Patellar Component

All components must be cemented with respect to the bone.

Exchange of the Triathlon PSR Tibial Insert for any reason constitutes a failure and study termination for the subject.

If revision of any other component occurs during the study, the event does not constitute a failure or study termination.

If the subject fails to return for his/her follow-up appointments, every effort should be made to contact the subject to assess his/her health status. If, after attempting to contact the subject through three documented phone calls and a certified letter, the subject still does not respond, he/she will be considered lost to follow-up. A Study Termination eCRF will be completed only after notifying Stryker of the subject's status and being given approval to terminate.

In the event a subject does not have surgery, Stryker should be contacted to discuss if/when the surgery will be rescheduled. Preoperative data must be current within 4 months of the study surgery and will need to be re-collected if the surgery is rescheduled more than 4 months from the initial data collection. If the surgery is not to be rescheduled or if the subject is no longer

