5.2 Radiographic Outcomes

Radiographs will be taken and collected in the anteroposterior (AP), mediolateral (ML), and merchant views for the preoperative, 6-week, 1-, 2-, 5, and 10-year intervals. The suggested radiographic technique for the views required is included in **Appendix D**.

Radiographs will be evaluated by an independent reviewer throughout the course of the study. Parameters for radiographic failures will follow the guidelines that have been set by the Knee Society⁸. Radiographic analysis of the tibial component will employ seven zones (Zone 1 – Zone 7) in the AP view and three zones (Zone 1 – Zone 3) in the lateral view. Radiographic analysis of the femoral component will employ seven zones (Zone 1 - Zone 7) in the lateral view. Radiographic analysis of the patellar component will employ five zones (Zone 1 – Zone 5) in the merchant view. Numerous parameters will be reviewed including radiolucency, gaps and subsidence. Radiolucency in at least 50% of a zone and measuring at least 1 mm in width is defined as radiolucency present. Subsidence is defined as settling of the prosthetic component in bone and, for this study, is measured by looking at the change in position of the tibial baseplate with reference to a bony landmark (usually the very margin of the tibia) between visit

intervals. Cases that present with tibial baseplate subsidence of greater than 5 mm or at least 2 mm radiolucencies in all zones within a single view will be considered radiographic failures.

6 Adverse Events

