8.1.2 Secondary Objective Analyses

The Kaplan-Meier survival curve of all-cause revision and removal of the Triathlon PSR insert will be displayed using SAS/PROC LIFETEST at 10-years postoperative. The survival rate at 10 years will be presented with a 95% CI.

The ROM at 2 years will be compared with 124 degrees, as derived from Triathlon PS study, using an equivalence margin of 5 degrees. A TOST (two one-sided test) will be used with SAS/PROC TTEST to test the difference.

The change between the preoperative and postoperative EQ-5D TTO scores will be tested with Paired T-tests.

The analysis for the additional data collected is in **Section 8.4.1**.

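### Radiographic failure is reported only visit by visit, so the 5- and 10-year percentages are prevalences among knees still followed, and no planned output gives cumulative radiographic failure

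*Combined protocol and SAP*

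**What the plan says.** Section 5.2 schedules films in the AP, ML and "merchant views for the preoperative, 6-week, 1-, 2-, 5, and 10-year intervals". It defines the endpoint by image criteria read by an independent reviewer: "Cases that present with tibial baseplate subsidence of greater than 5 mm or at least 2 mm radiolucencies in all zones within a single view". Knees meeting either criterion count as failed on radiographs.

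Section 8.4.1 sets the reporting basis: "Radiographic data will be presented for each visit interval at which radiographs are collected". The next sentence extends it to the endpoint: "The frequency and percentage of radiographic failures will also be presented accordingly". It states no denominator and no cumulative or time-to-event summary. Section 8.3 rules out imputation, and nothing provides for carrying a failed status forward.

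Section 4.3 treats two kinds of revision differently. For the insert: "Exchange of the Triathlon PSR Tibial Insert for any reason constitutes a failure and study termination for the subject". For everything else: "If revision of any other component occurs during the study, the event does not constitute a failure or study termination".

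Revision is handled elsewhere. In Section 8.1.2, "The Kaplan-Meier survival curve of all-cause revision and removal of the Triathlon PSR insert will be displayed", with a 95% CI at 10 years. Section 8.2.1 makes revision or removal of any component a safety parameter, and Section 11.3 says revision/removal rates will be tabulated. The Synopsis lists radiographic outcomes under additional data collection, not among the objectives.

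**The concern.** A knee that meets the Section 5.2 definition at one film and then has its insert exchanged has no later study films. It is counted at the visit where failure was seen and is absent from every table after that. A knee that fails and is exchanged between two scheduled films, for instance between 2 and 5 or between 5 and 10 years, appears in no radiographic count. This would happen even with perfect follow-up of everyone else.

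The late percentages therefore answer a different question from the one most readers will ask. They give the share of knees still under observation that are currently in a failed state, not the share that ever failed. Section 10 plans publications at 2 and 10 years, and a 10-year percentage of radiographic failures is easily read as a 10-year failure rate. If failed knees have the insert exchanged more often than other knees, the figure errs in the device's favour.

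**Working it through.** **Is there a figure to reproduce?** Not for this endpoint. The documents give no expected radiographic failure rate, no share of failed knees whose insert is exchanged, and no time from failure to exchange. The size can only be shown as a range under stated assumptions.

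**Step 1: the visit percentage.** Let F be the true cumulative proportion with radiographic failure by a visit, and r the share of those failed knees whose insert was exchanged before that visit. Both are assumptions. Take other losses as unrelated to failure, and insert exchange in knees without radiographic failure as negligible. Then

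visit percentage = F(1 − r) / (1 − F·r).

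This cannot exceed F, and for small F it is about (1 − r) times F.

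**Step 2: numbers at 10 years, F = 5%.**

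| r | Calculation | Visit percentage |
|---|---|---|
| 0 | 0.05 / 1 | 5.0% |
| 0.2 | 0.040 / 0.990 | 4.04% |
| 0.5 | 0.025 / 0.975 | 2.56% |
| 0.8 | 0.010 / 0.960 | 1.04% |
| 1 | 0 / 0.950 | 0% |

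With r = 0.5, F = 1% gives 0.005 / 0.995 = 0.50%, and F = 10% gives 0.05 / 0.95 = 5.26%. For scale, 5% of 200 knees is 10 knees. The gap for F = 5% therefore runs from 0 to 5 percentage points, or 0 to 10 knees per 200.

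**Step 3: how far timing matters.** Two assumed patterns, both with 5% cumulative failure at 10 years, give very different answers.

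- *Milder.* Cumulative failure is 0.5%, 1%, 2.5% and 5% at 1, 2, 5 and 10 years. A share of the failures present at one film is exchanged before the next, and no new failure is exchanged before it is first seen. The 10-year visit then shows 4.31% (share 0.2), 3.49% (0.5) or 2.89% (0.8).
- *More severe.* Failure has constant rate λ = −ln(0.95)/10 = 0.00513 per year, and every failed knee goes on to exchange at constant rate μ. The failed and unexchanged share at time t is A = λ/(μ − λ) × (e^(−λt) − e^(−μt)), and the visit percentage is A / (A + e^(−λt)). With a mean of 2 years to exchange (μ = 0.5), t = 10 gives A = 0.01036 × (0.9500 − 0.0067) = 0.00978, and 0.00978 / 0.95978 = 1.02%. At 5 years the same formula gives 0.94%, against a cumulative 2.53%. Means of 4 years and 1 year give about 1.9% and 0.5% at 10 years.

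The documents do not favour either pattern.

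**Step 4: does another planned output fill the gap?** The Kaplan-Meier curve counts insert revision and removal, so it omits radiographic failures that are never exchanged and does not mark which exchanges followed one. The safety tabulations count adverse events and revisions. Neither gives the proportion of knees that ever met the Section 5.2 definition.

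**The case against.** The strongest reply is that this is descriptive information. No hypothesis, margin or decision uses it, and a by-visit summary is what Section 8.4.1 applies to additional data generally. That stands, and it limits the importance of the point.

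It can also be said that exchanged knees are not hidden. Insert revision or removal for any cause is a secondary objective with a 10-year Kaplan-Meier estimate, and revision of any component enters the safety reporting. Operative-site adverse events are reportable at any time under Section 6.1. This also stands. (Section 8.4.4, read literally, limits secondary analyses to subjects available at 2 years, which is a separate question and is not relied on here.) What remains missing is one count: failures by the image definition, exchanged or not.

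Four stronger readings are tempting and are not supported:

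- A reader might infer that the late percentages will be far below the cumulative rate. The documents supply neither F nor r, and Step 2 runs from no understatement to complete understatement.
- A reader might infer that any revision removes the knee. Section 4.3 ends participation only for insert exchange.
- A reader might infer that the by-visit percentage will stay flat or fall over time. In the milder pattern of Step 3 it rises at each visit; with a share of 0.5 it is 0.5%, 0.75%, 1.89% and 3.49%.
- A reader might infer that revisions should simply be counted as radiographic failures. That would add knees never shown to meet the Section 5.2 image criteria and would overlap the Kaplan-Meier endpoint.

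The denominator is also not written down. That it consists of knees with a film at the visit is the natural reading of Section 8.4.1, not a stated rule.

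**Conclusion.** The point holds as a gap in a descriptive endpoint. As planned, the 5- and 10-year radiographic percentages are prevalences among knees still followed with the original insert, and no output gives cumulative radiographic failure. The direction is understatement, provided that other losses are unrelated to failure and that failed knees have the insert exchanged more often than others. The size is not determined by the documents. With an assumed 5% cumulative failure it runs from nothing (5.0% shown) through about half (2.6% shown when half are exchanged) to all of it (0% shown). The primary and secondary analyses are unaffected.

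**What to change.** In Section 8.4.1:

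1. State the denominator for the radiographic percentage at each visit, and keep the by-visit table as descriptive.
2. Add the cumulative proportion of knees with a first radiographic failure by the Section 5.2 definition, at 2, 5 and 10 years with a 95% CI. Once a knee has failed, it stays counted.
3. Use an interval-censored or cumulative-incidence method, since failure is seen only at widely spaced films. Treat insert exchange before any observed failure as a competing event.
4. As a separate sensitivity line, show a composite that also counts insert exchange or component revision for loosening or subsidence. Item 2 still cannot see a failure that arises and is exchanged between films. The composite shows how much that could matter without altering the image-based definition.

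The cost is SAP wording and one extra table from data already collected. The downside is a possibly less favourable reported figure.

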8.4.2 Sample Size Justification

Based on the Triathlon PS clinical study, it is reasonable to have a SF36 PCS reference value of 47.3 (with a standard deviation of 10.7) at 2-years postoperative. Two hundred cases are needed to have a power of 95% to detect that the mean SF36 PCS at 2-years postoperative is non-inferior to the reference value with a margin of 2.5 at 5% significance level. After factoring in a 20% lost to follow-up rate, a total of 250 cases will be needed.

8.4.3 Interim Analyses

No interim analysis is planned.

8.4.4 Analysis Population

Per Protocol Population:

The study population for analysis will include all non-censored subjects who received a cemented Triathlon Total Knee with the Triathlon PSR insert and are available for primary objective evaluation at the 2-year primary endpoint.

The primary and secondary objective analyses will be based on the per protocol population.

Safety Population:

The safety population will include all non-censored subjects who received a cemented Triathlon Total Knee with the Triathlon PSR insert.

9 Study Monitoring, Auditing, and Inspecting

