8.2 Safety

8.2.1 Safety Parameters

Safety parameters include all protocol-defined adverse events as well as all-cause revision and/or removal of any component of the Triathlon Total Knee with the Triathlon PSR Insert. For details regarding protocol-defined adverse events, see **Section 6.1**.

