11.3 Expected Complications

Complications associated with TKA procedures, such as those performed with the study device, have been reported. These include the potential for but are not limited to: infection, genitourinary disorders, gastrointestinal disorders, vascular disorders, bronchopulmonary disorder, myocardial infarction, injury to the knee's neurovascular structures, loosening of the components, osteolysis, heterotopic bone formation, deep vein thrombosis, pulmonary embolism, metal sensitivity reactions, intraoperative or postoperative fracture of the femur, patella or tibia, and the need for re-operation, revision, arthrodesis of the involved joint, amputation of the limb and death. The safety analysis will include tabulation of AE rates as well as revision/removal rates.

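### The 10-year insert survivorship curve is restricted to cases available at the 2-year evaluation, so earlier revisions drop out and survival is overstated by about the 2-year revision risk

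*Combined protocol and SAP*

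**What the plan says.** The Study Synopsis lists survivorship of the PSR insert at 10 years among the secondary objectives. Section 8.1.2 specifies a Kaplan-Meier curve for revision or removal of the insert from any cause and adds: "The survival rate at 10 years will be presented with a 95% CI". It names no analysis population.

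Section 8.4.4 supplies one: "The primary and secondary objective analyses will be based on the per protocol population". Subjects in that population must be *non-censored*, must have received the cemented construct with the PSR insert, and must be subjects who "are available for primary objective evaluation at the 2-year primary endpoint". The Evaluation Schedule sets the 2-year window at plus or minus 2 months.

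Section 4.3 states: "Exchange of the Triathlon PSR Tibial Insert for any reason constitutes a failure and study termination for the subject". The termination is dated at the procedure. The same section lists the components of which "it is required that the following components are implanted to be included in the analysis".

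Revisions also appear under safety. Section 8.2.1 counts "all-cause revision and/or removal of any component of the Triathlon Total Knee with the Triathlon PSR Insert" as a safety parameter, and Section 11.3 says: "The safety analysis will include tabulation of AE rates as well as revision/removal rates". The population for those analyses is defined in 8.4.4: "The safety population will include all non-censored subjects who received a cemented Triathlon Total Knee with the Triathlon PSR insert". The plan does not define *non-censored* anywhere.

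**The concern.** The event that Section 4.3 calls a failure removes the subject from the analysis meant to count failures. A subject whose insert is exchanged at, say, 9 months is terminated and has no 2-year evaluation. That subject is outside the per-protocol population and so outside the curve. Every case that does enter is known to have been unrevised up to its 2-year evaluation. This is immortal-time selection: the curve is flat by construction until the visit window opens at 22 months.

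The reported 10-year figure and its 95% confidence interval would then describe inserts that had already survived about two years, under a label that says survival from surgery. Section 10 anticipates a 10-year multi-center publication, and Section 11.5 says the study is meant to inform clinicians by comparison with published results for similar devices. A figure conditional on two revision-free years does not serve that comparison.

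**Working it through.** **The plan's own figures.** The plan gives no figure for survivorship. Its sample size, which supplies the 250 cases and 20% loss used below, reproduces. With SD 10.7, margin 2.5, one-sided 5% and 95% power (Section 8.4.2), n = (10.7 × (1.645 + 1.645) / 2.5)² = 198.2. The exact t calculation gives 200, with power 95.03%, and 200 / (1 − 0.20) = 250.

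**What the restricted curve estimates.** Let S(t) be the probability that the insert is unrevised at t years from surgery, and F(t) = 1 − S(t). If only cases unrevised and in follow-up at about 2 years are kept, and loss is unrelated to revision, Kaplan-Meier estimates S(10)/S(2). The overstatement is

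S(10)/S(2) − S(10) = F(2) × S(10)/S(2),

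which is always a little below F(2).

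**Inputs.** The documents give no revision rates, so F(2) and F(10) below are assumptions for illustration.

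| F(2) / F(10) | True S(10) | S(10)/S(2) | Overstatement (points) |
|---|---|---|---|
| 0.5% / 2.5% | 97.5% | 0.975/0.995 = 98.0% | 0.5 |
| 1% / 3% | 97.0% | 0.97/0.99 = 98.0% | 1.0 |
| 2% / 4% | 96.0% | 0.96/0.98 = 98.0% | 2.0 |
| 3% / 6% | 94.0% | 0.94/0.97 = 96.9% | 2.9 |

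The first three rows have different true survival, yet all would be reported as 98.0%: the curve cannot separate devices that differ only in early failure. Over a wider assumed range (F(2) from 0.5% to 4%, F(10) from 2% to 10%), the same formula gives 0.49 to 3.83 points.

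**Simulation with the visit window and loss.** Assumptions: 250 cases; 2-year evaluation uniform on 22 to 26 months; 20% lost by 2 years (rate from Section 8.4.2, timing assumed); 5% lost per year after that (assumed); loss independent of revision; 4,000 replicates.

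| F(2) / F(10) | Mean overstatement (points) | Observed revisions left out | Mean 95% half-width, per-protocol curve (points) |
|---|---|---|---|
| 0.5% / 2.5% | 0.5 | 1.1 | 2.1 |
| 1% / 3% | 1.0 | 2.3 | 2.1 |
| 2% / 4% | 1.9 | 4.4 | 2.1 |
| 3% / 6% | 2.9 | 6.6 | 2.6 |

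About 195 to 199 of the 250 cases enter the per-protocol curve. The window matters little: revisions before 24 months that stay in because the evaluation came earlier are 0.5% to 1.1% of observed revisions. A separate simulation with lighter later loss (a further 20% by 10 years) and F(2)/F(10) of 1%/4%, 2%/5% and 3%/6% gave overstatements of 0.97, 1.97 and 2.92 points.

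**The term *non-censored*.** Suppose it also removes everyone lost before 10 years. In the four scenarios above, simulated with 1,000,000 cases each:

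| True S(10) | Per-protocol curve | Error (points) | Safety Population curve | Error (points) |
|---|---|---|---|---|
| 97.5% | 97.5% | 0.0 | 96.7% | −0.8 |
| 97.0% | 97.5% | +0.5 | 95.9% | −1.1 |
| 96.0% | 97.4% | +1.4 | 94.2% | −1.8 |
| 94.0% | 96.1% | +2.1 | 91.4% | −2.6 |

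Removing lost subjects takes event-free time out of the risk set. This partly offsets the first bias in the per-protocol curve. In the Safety Population it produces a bias in the other direction, so moving the curve to that population without changing its definition does not cure the problem.

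**The case against.** The best defence is that the sentence in 8.4.4 was written with the 2-year endpoint in mind. Section 8.1.2 sets no lower time limit on revisions, Section 4.3 counts insert exchange for any reason as a failure, and the component rule in 4.3 could be read as the real condition for being analysed. An analyst following those sections might well include early failures. That may be the intention, but neither section lifts the 2-year condition, and 8.4.4 is the only place that assigns a population to the secondary analyses.

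It is also true that early revisions do not vanish from the report, because the safety tabulation covers them. That tabulation is a crude rate for any component. It takes no account of follow-up time and does not answer the insert survivorship objective.

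On size, the defence has real points. Few knees are involved. The bias is below the half-width of the interval in three of the four scenarios. Survivorship is descriptive, with no margin or performance goal. The size depends on assumed rates, on loss being independent of revision and on the meaning of *non-censored*; under one reading the error at the lowest assumed rates is nil. These points limit the severity. They do not remove the defect, because the bias is systematic and the interval is centred on the wrong quantity.

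**Conclusion.** The concern holds. Followed as written, the plan puts the 10-year survivorship curve on cases already known to be unrevised at about 2 years, and the result approximates S(10)/S(2) rather than S(10). If *non-censored* removes nobody further and loss is unrelated to revision, the error favours the device and is just under the 2-year revision risk: 0.5 to 2.9 points for assumed 2-year risks of 0.5% to 3%. If *non-censored* also removes subjects lost before 10 years, the per-protocol error is 0.0 to +2.1 points. That the text excludes early revisions is clear; the size is illustrative, because the documents give no revision rates. The primary objective and the sample size are not affected. This should be fixed before analysis, but it does not threaten the study's main conclusion.

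**What to change.** In Section 8.4.4, give the survivorship analysis its own population and rules:

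- **Population:** all enrolled cases that received the cemented Triathlon construct with the PSR insert and the components required by Section 4.3, with no condition on 2-year availability.
- ***Non-censored*:** delete it for this analysis, or define it so that no subject with follow-up is removed.
- **Time zero:** date of surgery.
- **Event:** revision or removal of the PSR insert at any time.
- **Censoring:** at death, or at the last date the insert was known to be in place. As a clarification, say that the sponsor-approval date entered on the termination form for subjects lost to follow-up is not the censoring date.

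Keep the 2-year-available population for the 2-year SF-36 and ROM analyses. The cost is SAP wording only, since the visits and follow-up questionnaires already collect the data. Reported survival will be slightly lower.

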6.1 Reporting of Adverse Events

The AE reporting requirements for this study are as follows:

[figure not shown]
- All AEs that meet the definition of serious (see page 22) and occur within the perioperative period (intraoperative to hospital discharge) to 90 days postoperative
- All AEs related to the operative site, regardless of seriousness or time of occurrence

On postoperative functional evaluations, investigators and SCs will be prompted to question subjects as to whether they have seen a doctor for any reason, been hospitalized for any reason or have a current impediment to their function.

For the 6-, 7-, 8-, 9-year intervals, only a Follow-up Questionnaire will be administered. SCs will be responsible for following up with the subjects regarding any questionable responses received on the Follow-up Questionnaire. If it is determined upon this further investigation that a protocoldefined AE has occurred, the SC will be responsible for completing an AE eCRF, submitting the event to Stryker, and reporting the event to the IRB as required.

The following decision tree facilitates identification of AEs for which reporting is required under this study protocol:

Figure 1. Adverse Event Decision Tree

General Physical Examination Findings

At screening for inclusion into the study, any clinically significant abnormality should be recorded as a preexisting condition and reported on the Demographics eCRF. From the time of consent forward, any new clinically significant findings or abnormalities that meet the definition of a protocol defined AE must also be recorded and documented as an AE.

Adverse Event Reporting Period

The study period during which AEs must be reported is normally defined as the period from the initiation of any study procedures to the end of the study treatment follow-up. The start of study procedures is considered to be the point of consent. Any AEs which fit the protocol defined reportable events must be reported from the time of consent until study completion.

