6.3 Study Sponsor Notification by Investigator

Of reportable AEs, certain events must be submitted to Stryker within 24 hours for timely notification:

Adverse events that require time sensitive reporting:

An adverse event should be reported to Stryker Clinical Research either by telephone/fax/email within 24 hours of the site becoming aware of the event if any of the following apply:

- The AE occurs intraoperatively or is related to the surgical procedure.
- The AE is considered by the investigator to be device related or if the investigator is uncertain regarding the device related assessment;
- The AE required a reoperation of the study knee or a revision of any study knee components.

At the time of the initial report, the following information should be provided:

Subject number	Whether study treatment was
 A description of the event 	discontinued
Date of onset	 Investigator assessment of the
Current status	association between the event and
	the study treatment

An AE eCRF for an AE meeting the criteria above should be completed within 24 hours of the investigative center's awareness, and the de-identified source documentation should be submitted to Stryker within 24 hours of the investigative center's awareness. These reports will be evaluated by Stryker to determine if a Product Inquiry (PI) is required.

It is recommended that all other reportable AEs are submitted through eCRF entry within 2 weeks.

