8.2.2 Safety Analyses

The frequency and percentage of all protocol-defined adverse events will be tabulated. All protocol-defined adverse events will be tabulated, and a 95% CI will be presented. For details regarding protocol-defined adverse events, see **Section 6.1**.

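### An adverse event that leads the surgeon not to implant the PSR insert is collected, but falls outside the only safety population the plan defines

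*Combined protocol and SAP*

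**What the plan says.** **What is collected.** Section 6.1 states: "Any AEs which fit the protocol defined reportable events must be reported from the time of consent until study completion". Two classes of event are reportable. The first is serious AEs that "occur within the perioperative period (intraoperative to hospital discharge) to 90 days postoperative". The second is "All AEs related to the operative site, regardless of seriousness or time of occurrence". Section 6.3 asks for notice to the sponsor within 24 hours when, among other triggers, "The AE occurs intraoperatively or is related to the surgical procedure".

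**What happens when the insert is not implanted.** The list of withdrawal reasons and termination dates in Section 4.3 has the row "Study device not implanted Date of surgery". The same section continues: "At the time of study surgery, it is required that the following components are implanted to be included in the analysis". It then names the PSR insert and compatible baseplate, PS femoral and patellar components, all cemented. Under Number of Cases in the synopsis, only cases that receive the device count toward the 250.

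**What is analysed.** Section 8.2.2 states: "The frequency and percentage of all protocol-defined adverse events will be tabulated". It adds a 95% confidence interval but names no population. Section 8.4.4 defines one safety population: "The safety population will include all non-censored subjects who received a cemented Triathlon Total Knee with the Triathlon PSR insert". The plan defines no set of attempted surgeries and no listing for subjects whose surgery ended without the insert.

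**The concern.** Entry to the safety population depends on how the operation turned out. Section 11.2 foresees intraoperative fissure, fracture or perforation of the femur or tibia, and Section 11.3 lists intraoperative fracture of the femur, patella or tibia. If such an event makes the surgeon choose another construct, the subject leaves the safety denominator because of the event that a safety analysis should show.

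The rates at stake are the perioperative and 90-day ones. Section 6.1 says that the collected events will be compared with published data, and that rates are expected to be comparable to those of historical Triathlon PS constructs. A rate among recipients answers a narrower question than the risk of setting out to implant the PSR insert. A reader of the final report could not tell how far the two differ, because the plan requires no count of attempted cases.

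**Working it through.** **1. The plan's own figure.** Section 8.4.2 gives an SD of 10.7, a margin of 2.5, a 5% significance level (one-sided, matching the lower bound of a 90% interval) and 95% power.

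- Normal approximation: n = (10.7 × (1.645 + 1.645) / 2.5)² = 198.2, so 199.
- Noncentral t: power is 94.95% at n = 199 and 95.03% at n = 200, which matches the stated 200.
- With 20% loss: 200 / (1 − 0.20) = 250.

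The sample size reproduces. The 250 count recipients only, so nothing below changes it.

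**2. One subject followed through the sections.** Suppose an intraoperative fracture occurs and the surgeon implants another construct.

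| Step | Section | Consequence |
|---|---|---|
| Is the event reportable? | 6.1, 6.3 | Yes, with 24-hour notice to the sponsor |
| Is that event followed? | 6.1, 6.4 | Yes, to resolution or stabilization |
| Termination date | 4.3 | Day of surgery |
| New serious AEs to day 90 | 4.3 with 6.1 | Unclear, because the subject may already be terminated |
| Counts toward the 250? | Synopsis | No |
| Included in the analysis? | 4.3 | No |
| In the safety population? | 8.4.4 | No |
| In the AE table? | 8.2.2 | Yes if "all" is taken literally; no if 8.4.4 supplies the denominator |

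The last row is the conflict. A percentage and a confidence interval need a denominator, and the only one defined excludes this subject. The conditions for analysis in 4.3 and 8.4.4 also differ in form: 4.3 lists four components including the patellar one, while 8.4.4 names the cemented knee with the PSR insert.

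**3. How many surgeries could be left out.** The documents give no non-implantation rate p, so p is assumed. Attempts needed for 250 recipients = 250 / (1 − p), rounded up.

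| Assumed p | Attempts | Left out |
|---|---|---|
| 1% | 252.5, so 253 | 3 |
| 2% | 255.1, so 256 | 6 |
| 3% | 257.7, so 258 | 8 |
| 4% | 260.4, so 261 | 11 |

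**4. How far a rate could move.** Assume 5 events of one type among 250 recipients: 5/250 = 2.0% (exact 95% CI 0.65% to 4.61%). Take p = 1%, so that 3 subjects are left out.

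- None had the event: 5/253 = 2.0%.
- Two had it: 7/253 = 2.8% (1.12% to 5.62%).
- All three had it: 8/253 = 3.2% (1.37% to 6.14%).

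The rate is understated only if subjects left out had the event more often than recipients. Both the 5 events and the split among those left out are assumptions.

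**The case against.** The strongest reply is that safety oversight is intact and a recipient-based set is a defensible choice for a post-market study of a cleared device. Intraoperative AEs go to the sponsor within 24 hours (6.3) and to the ethics committee or IRB as it requires (6.3.1). They may lead to a formal investigation (6.5), and non-implantation may be logged as a major deviation (7.6). No safety hypothesis is tested. All of this stands, and it limits the point to planned tabulation and to new events after termination.

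Several stronger readings are tempting, but the documents do not support them:

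- **A reader might infer that these events reach no safety table.** Section 8.2.2 taken alone would include them. Exclusion is the natural result of reading it with 4.3 and 8.4.4, but no section states it.
- **A reader might infer that follow-up stops on the day of surgery.** Section 4.3 is permissive about withdrawal, and 6.1 and 6.4 keep an event that has already occurred under follow-up. Only new events are in doubt.
- **A reader might infer that the excluded events relate to the insert's reduced rotational constraint.** Sections 1.1 and 3.1 place that reduction in deep flexion, and 11.2 attributes intraoperative fracture to impaction of the component. The link is conjecture, and the selection argument does not need it.
- **A reader might equate subjects left out with hidden events.** Non-implantation can have other causes, such as a need for Size 0 (not used in this study, Section 3.1) or a choice of uncemented fixation. Section 3.2 also allows augments and stems, so a bone problem need not rule out the insert.
- **Reporting from consent adds little before surgery.** The serious-AE window opens intraoperatively, so only operative-site events are reportable earlier.

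The documents also do not say whether the historical or published rates count recipients or attempts. Replacing the recipient set could therefore create a mismatch. It would also pool the 90-day events of subjects who received a different construct. This is a good reason to keep that set for the main rates.

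**Conclusion.** The point holds as a gap between 4.3, 8.2.2 and 8.4.4. An AE that leads to non-implantation is collected and followed but falls outside the only defined safety denominator, and new serious AEs to day 90 in that subject may not be captured. The bias, if any, lowers perioperative rates when subjects left out had more events than recipients.

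Its size cannot be estimated from the documents. The range of about 3 to 11 attempted surgeries rests wholly on an assumed 1% to 4% non-implantation rate, and it counts surgeries, not events. A reader might go on to infer that the reported complication rate is some fixed fraction of the true one. That needs a complication rate and a switching fraction that the plan does not give.

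The primary comparison, the per protocol and survivorship sets, and the 200 and 250 cases are unaffected. This is an inexpensive improvement to safety reporting and does not threaten the trial's main conclusion.

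**What to change.** 1. **Section 8.2.2:** name the recipient-based safety population as the denominator for the main AE rates, and align the implantation conditions in 4.3 with 8.4.4.
2. **Sections 8.2.2 and 8.4.4:** report the number of surgeries attempted, implanted and not implanted, with the reason for each non-implantation.
3. **Section 8.2.2:** add a separate table of protocol-defined AEs in subjects whose index surgery began with intent to implant the PSR insert but who did not receive it.
4. **Section 4.3:** continue protocol-defined AE reporting for these subjects to day 90 before study termination.

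The cost is a wording change to the protocol and its statistical section, and AE reporting for a few extra subjects who do not count toward the 250. Reported safety may look slightly less favourable.
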